6.3.2.4. Sustained dryness

Definition

Firstly, the proportion of patients with fluid present at baseline will be identified as patients with IRF or SRF equal to "Yes" at baseline and it will be presented together with the distribution of patients in the following categories: patients with only IRF present at baseline, patients with only SRF present at baseline and patients with both IRF and SRF at baseline.

Among patients with fluid present at baseline, patients with fluid resolution will be identified in case of absence of IRF and SRF and patients without fluid resolution will be also categorized in 'Only IRF present', 'Only SRF present', 'Both IRF and SRF present' at each post-baseline applicable timepoint from Week 8 to Week 48 considering patients who performed SD-OCT at the corresponding timepoint. Then patients who achieved the sustained dryness will be identified considering patients with fluid resolution for at least 2/3 consecutive visits.

| | |
|--|---|
| | Statistical Analysis Plan |
| | Sponsor: Novartis Protocol: CRTH258AIT04 |

For each possible timepoint from Week 8 to Week 48, the sustained dryness will be evaluated considered the SD-OCT assessment as follows:

- If patient perform the visit: the assessment done at the specific timepoint and the previous one performed.
- If patient does not perform the visit: the previous 2 assessments performed will be considered.

The time to achieved sustained dryness is defines as the time, in weeks, from the first injection (i.e., baseline visit) to the earliest post-baseline SD-OCT assessment date on which the first sustained dryness is reached. If a patient does not achieve sustained dryness, the time will be censored at the date of last SD-OCT assessment.

Time to sustained dryness is computed as:

$$(\text{event}/\text{censoring date} - \text{first injection date} + 1)/7$$

where event date is SD-OCT date in which the first sustained dryness is reached while censor date is the last SD-OCT date.

Analysis methodology

Firstly, a description of the proportion of patients with IRF or SRF present at baseline will be provided. On these patients a description of the proportion of patients with fluid resolution, defined as absence of IRF and SRF fluid, will be provided at each timepoint considered the number of patients who perform each visit. A graphical representation (bar graph) will be also provided.

The cumulative incidence rate of patients with sustained dryness from Week 8 up to Week 48 will be summarized together with 95% confidence interval (CI) using the Clopper-Pearson method. A graphical representation (bar graph) will be also provided.

The median time to achieve sustained dryness and its corresponding two-sided 95% confidence interval (CI) will be estimated using the Kaplan-Meier product-limit method. Reverse Kaplan-Meier plot will be also presented.

Data handling rules

An observed approach will be considered.

Sensitivity of secondary analysis

Not applicable.

| | |
|--|----------------------------------|
| | Statistical Analysis Plan |
| | Sponsor: Novartis |
| | Protocol: CRTH258AIT04 |

6.3.2.5. Reason underlying the Investigators' choice of brolucizumab treatment regimen at Week 16

Definition

As previously investigated during the interim analysis, the reasons underlying the Investigators' choice of brolucizumab treatment regimen at Week 16 will be analyzed.

According to SmPC of brolucizumab, after the loading phase of treatment (i.e., first 3 injection every month) at Week 16 the investigator should choice the treatment regimen for each patient between the q12w or the q8w regimen. This choice should be based on the presence/absence of disease activity evaluated according to different parameters.

Analysis methodology

Considering the safety set and the number of patients who performed Week 16 and were still on treatment, a description of the total number of parameters considered to assess the presence or absence of disease activity at Week 16 will be provided in terms of continuous variable and frequencies of each combination of parameters considered to assess disease activity will be also provided (e.g., BCVA+CSR, CST+IRF and so on). Considering the total number of patients who performed Week 16 and were still on treatment, the proportion of patients for whom their disease activity is evaluated by means of each one of the following parameters is summarized:

- BCVA
- Leakage at FA/ICGA
- Central Subfield Thickness (CST) at SD-OCT
- Intraretinal fluid (IRF) at SD-OCT
- Subretinal fluid (SRF) at SD-OCT
- Subretinal pigment epithelium (sub-RPE) fluid at SD-OCT
- Retina Pigment Epithelial Detachment volume at SD-OCT
- Central Retinal Thickness (CRT)
- Subretinal hyperreflective material (SHRM) at SDOCT
- CNV size at OCTA
- Vessel density at OCTA
- Vessel morphology at OCTA
- Hemorrhage at CFP
- Other

A graphical representation of the proportion of patients with disease activity evaluated by means of each parameter will be also provided by means of graph bar.

| | |
|--|----------------------------------|
| | Statistical Analysis Plan |
| | Sponsor: Novartis |
| | Protocol: CRTH258AIT04 |

These results (i.e., both proportion and bar graph) will be provided overall and according to the final regimen choice reported by the Investigator (i.e., q12w or q8w).

The parameters used for the regimen choice will be also classified in the following categories:

- BCVA
- Leakage at FA/ICGA
- SD-OCT parameters (i.e., Central Subfield Thickness (CST), Intraretinal fluid (IRF), Subretinal fluid (SRF), Subretinal pigment epithelium (sub-RPE) fluid, Retina Pigment Epithelial Detachment volume, Subretinal hyperreflective material (SHRM), Central Retinal Thickness (CRT))
- OCTA parameters (i.e., CNV size, Vessel density, Vessel morphology)
- Hemorrhage at CFP
- Other

The proportion of patients evaluated by means of each category will be described and graphically represented.

In addition, multivariate logistic regression model will also be implemented to evaluate which of these factors are determinants for the selection of the dosing regimen at Week 16. The response variable will be the treatment regimen assigned to each patient (q12w or q8w), while the covariates included in the model will be the categories of parameters used to take the regimen choice according to the group presented above.

Considering the safety set and the number of patients who performed Week 16 and were still on treatment, descriptive statistics of SD-OCT parameters and predominant type CNV lesion at baseline will be provided considering:

- BCVA groups based on BCVA changes at Week 12: 'BCVA improvement' if change from baseline at Week 12 was greater or equal to 5 letters, 'BCVA stable' if change from baseline at Week 12 was between -5 and +5 letters and 'BCVA worsening' if change from baseline at Week 12 was lower or equal to -5 letters.
- CST groups based on CST changes at Week 12: '<0' and '>=0'.

Data handling rules

No missing imputation will be performed.

Sensitivity of secondary analysis

Not applicable.

| | |
|--|----------------------------------|
| | Statistical Analysis Plan |
| | Sponsor: Novartis |
| | Protocol: CRTH258AIT04 |

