At the Baseline visit (Day 1), after confirmation of eligibility, patients will be included and treated with intravitreal (IVT) brolucizumab at the dose of 6 mg. Only one eye could be treated in the study. Participants will receive three monthly loading doses of brolucizumab 6 mg at Baseline, Week 4 and Week 8, followed by a maintenance regimen every 12 weeks (q12w), which may be adjusted to a treatment regimen every 8 weeks (q8w) if disease activity (DA) in the study eye is detected according to Investigator's decision based on the disease activity assessments (DAAs) of visual and/or anatomical outcomes performed by the Investigator him/herself ("q12w/q8w regimen"). DA will be first assessed at Week 16 and then at each subsequent scheduled q12w/q8w treatment visit. In participants on q12w treatment regimen with DA occurrence at any of these visits, a q8w treatment regimen should be considered. If a

participant is adjusted to a q8w treatment regimen, he/she will subsequently be assessed at q8w treatment visits. In participants on q8w regimen without DA for two consecutive treatment visits, based on the Investigator's judgment, the re-allocation to a q12w treatment regimen should be considered. DAAs are to be performed by the Investigator based on visual acuity (BCVA) and/or 3-field CFP and/or one or more anatomical parameters assessed by SD-OCT and/or by OCTA, as per clinical practice. Of note, only those anatomical parameters that are instrumental to define DA in the Investigator's opinion will be recorded in the eCRF. All anatomical parameters collected by SD-OCT and OCTA throughout the study and by FA, ICGA (only for suspected PCV) and CFP at Screening and Week 48 (FA only) will be evaluated by an independent, treatment regimen-masked Central Reading Center (CRC) for the primary and secondary analyses at the end of the study. Of note, the Investigator will not be aware of the results of the CRC assessments during the study. For all participants, the last potential study treatment will be at the Week 44 visit or at the Week 48 visit, according to the different treatment regimen implemented.

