6.7.2 Instruction for prescribing and taking study treatment

The study consists of a treatment period with brolucizumab from Baseline (Day 1) up to Week 48, as shown in [Figure 6-1](#).

Figure 6-1 Treatment regimen

As per Beovu® SmPC, the recommended dose of 6 mg brolucizumab (0.05 ml solution) is to be administered by intravitreal injection every 4 weeks (monthly) for the first 3 doses. Thereafter, the Investigator may individualize treatment intervals based on DA in the study eye as assessed by visual acuity and/or anatomical parameters (BCVA and/or IRF, SRF, sub-RPE fluid, hemorrhage, CRT and/or OCTA parameters and/or 3-field CFP). A first DA assessment is to be performed at Week 16, as recommended in Beovu® SmPC. In participants without DA, treatment every 12 weeks (q12w) should be considered. In patients with DA, treatment every 8 weeks (q8w) should be considered. DA will be first assessed at Week 16 and then at each subsequent scheduled q12w/q8w treatment visit. In participants on q12w regimen with DA at any of these visits, a q8w treatment regimen should be considered. In participants on q8w regimen without DA for two consecutive treatment visits in the opinion of the Investigator, the re-allocation to a q12w regimen should be considered.

Regardless of treatment administration, Baseline, Week 4, Week 8, Week 12, Week 16 and Week 48 visits are mandatory for all participants. The timepoints of the other treatment visits will depend on the treatment regimen of each participant (q12w/q8w). No monitoring visits are planned between the injection visits.

For all participants, the last potential study treatment will be at the Week 44 visit or at the Week 48 visit, according to the different treatment regimen implemented.

The different types of visits occurring through the study are summarized in [Table 6-3](#) with a description of when disease activity assessment and treatment take place.

Table 6-3 Disease activity assessment and treatment occurrence according to visit type

Type	Disease Activity Assessment	Treatment
Screening visit	No	No
Baseline (Day 1) visit	No	Yes
Week 4 and 8 visits	No	Yes
Week 12 visit	No	No

Type	Disease Activity Assessment	Treatment
Week 16 visit	Yes	Yes (if DA is present)
Treatment visits (every 8 or 12 weeks according to Investigator's decision)	Yes	Yes (every 8 or 12 weeks according to Investigator's decision)
Week 48 visit	Yes	Only if a treatment was planned at the visit, based on treatment regimen

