8.3.1 Fluorescein angiography and indocyanine green angiography

Fluorescein angiography (FA) and indocyanine green angiography (ICGA) will be performed in both eyes at Screening and Week 48. All FA and ICGA images will be obtained by trained and study-certified site personnel at the study sites and evaluated by the Investigator according to his/her standard of clinical practice to confirm the diagnosis of wAMD at Screening. Certification of the equipment and examiners at each investigative site will occur prior to evaluation of study participants.

For the purpose of screening, FA and ICGA images from previous routine evaluations may be used as long as FA was performed within 3 days of the Screening visit using CRC-certified equipment and technician/Investigator.

A treatment regimen-masked Central Reading Centre (CRC) will be used in this study. The CRC will provide sites with a Study Manual and training materials for the specified study ocular images. Before any study images are obtained, site personnel, test images, systems and software will be certified and validated by the CRC as specified in the Study Manual. FA and ICGA screening images and FA images at week 48 will be forwarded to the CRC for independent standardized analysis. The CRC data will be used for the evaluation of the objectives comprising the assessment of FA and ICGA parameters (i.e. to classify the type of CNV lesions) to ensure a standardized evaluation. Further details about all parameters to be evaluated by the CRC are reported in the CRC grading charter (a separate document). The CRC will create a database with the agreed variables as indicated in the CRC charter and will transfer the data from this database to Novartis/CRO for analysis.

Additional images will be taken in case of any signs of intraocular inflammation. Fluorescein angiography should be performed for safety evaluation as described in Section 8.4.2. and uploaded onto the CRC portal.

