8.3.6 Disease activity assessments

The Investigator will perform a disease activity assessment (DAAs) on the study eye at Week 16 and at each subsequent scheduled q8w/q12w treatment visit. In participants on q12w treatment regimen with DA at any of these visits, a q8w treatment regimen should be considered. If a participant is adjusted to a q8w treatment regimen, he/she will subsequently be assessed at q8w treatment visits. In participants on q8w dosing regimen without signs of DA for two consecutive visits, based on the Investigator's judgment, the re-allocation to a q12w regimen should be considered. Of note, the Investigator will not be aware of the results of the CRC assessments at the time of performing each planned DAA.

DAAs are to be performed by the Investigator based on BCVA and/or one or more anatomical parameters detected by SD-OCT among IRF, SRF, sub-RPE fluid, hemorrhage, CRT and/or other OCTA parameters and/or 3-field CFP, as per clinical practice. The Investigator's assessed findings of both quantitative and qualitative SD-OCT and/or OCTA parameters will not be

captured in the eCRF but must be included in the source documents at the study site. Exclusively which of these parameters the Investigator considered instrumental to assess DA will be recorded in the eCRF.

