- Summary statistics of cumulative incidence of sustained dryness of the study eye will be provided by means of absolute and relative frequencies of participants with sustained dryness as defined above at each timepoint from Week 8 to Week 48. The binomial proportion and 95% confidence interval (CI) using the Clopper-Pearson method will also be provided.

To evaluate the reasons underlying the Investigators' choice of brolucizumab treatment regimen (q21w or q8w) at Week 16

The reasons underlying the Investigator's choice of brolucizumab dosing regimen (q12w or q8w) at Week 16 among BCVA and/or IRF, SRF, sub-RPE fluid, hemorrhage and/or CRT and/or OCTA parameters and/or 3-field CFP will be descriptively summarized. A multivariate logistic regression model will also be implemented in order to evaluate which of these factors are determinants for the selection of the dosing regimen at Week 16.

Further details will be provided in the Statistical Analysis Plan (SAP).

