| 3. To evaluate the effect of brolucizumab on the evolution of functional parameters of wAMD from Baseline to Week 48 | 3. BCVA ETDRS Score | 3. Change in BCVA from Baseline up to Week 48 |
| 4. To evaluate the effect of brolucizumab on sustained dryness from Baseline to Week 48 | 4. SD-OCT dates, Intraretinal fluid (IRF) and Subretinal fluid (SRF) | 
4. Time to reach sustained dryness of the study eye, as defined by the absence of IRF and SRF for at least 2 consecutive visits and for at least 3 consecutive visits
 
4. Cumulative incidence of sustained dryness of the study eye, i.e. the absence of IRF and SRF for at least 2 consecutive visits and for at least 3 consecutive visits
 |

| | |
|--|---|
| | Statistical Analysis Plan |
| | Sponsor: Novartis Protocol: CRTH258AIT04 |

| OBJECTIVES | VARIABLES | ENDPOINTS |
|--|---|--|
| 5. To evaluate the reasons underlying the Investigators' choice of brolucizumab treatment regimen (q21w or q8w) at Week 16 | 
5. Parameters considered to assess the presence of disease activity:
 
 • BCVA • Leakage at FA/ICGA • Central Subfield Thickness (CST) at SD-OCT • Intraretinal fluid (IRF) at SD-OCT • Subretinal fluid (SRF) at SD-OCT • Subretinal pigment epithelium (sub-RPE) fluid at SD-OCT • Retina Pigment Epithelial Detachment volume at SD-OCT • Central Retinal Thickness (CRT) • Subretinal hyperreflective material (SHRM) at SDOCT • CNV size at OCTA • Vessel density at OCTA • Vessel morphology at OCTA • Hemorrhage at CFP • Other | 5. Determinants in the Investigator's choice of brolucizumab dosing regimen (q12w or q8w) at Week 16 (i.e. BCVA, IRF, SRF, sub-RPE fluid, presence of hemorrhages, CRT, OCTA anatomical parameters and/or 3-field CFP) |
| 6. To evaluate anxiety/depression in patients with wAMD treated with brolucizumab | 6. HADS questionnaire | 6. Change in Hospital Anxiety and Depression Scale (HADS) scores from Baseline to Week 48 |
| 7. To evaluate quality of life in patients with wAMD treated with brolucizumab | 7. EuroQol-5D-5L questionnaire | 7. Change in EuroQol-5D-5L (EQ-5D-5L) scores from Baseline to Week 48 |

| | |
|--|---|
| | Statistical Analysis Plan |
| | Sponsor: Novartis Protocol: CRTH258AIT04 |

| OBJECTIVES | VARIABLES | ENDPOINTS |
|--|-------------------|--|
| 8. To assess the safety and tolerability of brolucizumab | 8. Adverse Events | 8. Incidence of Ocular and Non-ocular AEs throughout the study |

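### The Week 16 regimen model (SAP 6.3.2.5) relates q12w or q8w to which parameter categories were recorded as used, so its odds ratios should not be reported as determinants of the choice

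*SAP*

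**What the plan says.** Secondary objective 5 concerns the reasons behind the Investigator's choice of regimen at Week 16. Protocol 12.5.1 plans a descriptive summary of the reasons "among BCVA and/or IRF, SRF, sub-RPE fluid, hemorrhage and/or CRT and/or OCTA parameters and/or 3-field CFP will be descriptively summarized", followed by a logistic model to show which of these factors are determinants of the regimen.

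SAP 6.3.2.5 carries this out in two parts.
- **Description.** Fourteen parameters are tabulated as used or not used, overall and by regimen.
- **Model.** The response is the regimen assigned, and "the covariates included in the model will be the categories of parameters used to take the regimen choice according to the group presented above". There are six categories: BCVA, leakage at FA/ICGA, SD-OCT (seven items), OCTA (three items), hemorrhage at CFP, and other.

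On what is recorded, protocol 8.3.6 says: "Exclusively which of these parameters the Investigator considered instrumental to assess DA will be recorded in the eCRF". Protocol sections 8.3.2, 8.3.3 and 8.3.6 keep the Investigator's own SD-OCT and OCTA findings in the source documents and out of the eCRF.

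The meaning of a tick is worded in several ways. Protocol section 3 has "only those anatomical parameters that are instrumental to define DA". SAP 6.3.2.5 has "parameters considered to assess the presence or absence of disease activity at Week 16". SAP section 2 has "Parameters considered to assess the presence of disease activity".

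**The concern.** A determinant of the regimen would normally be a finding, such as fluid seen, a thicker retina or letters lost. The covariates here say only that a type of assessment was used. This regression is the only inferential analysis of objective 5 in the final SAP. The study's stated purpose is to support the choice between q12w and q8w. An odds ratio above 1 for SD-OCT, reported as a determinant, could be read as saying that some SD-OCT finding leads to q8w. The covariate does not contain that information. Values that could describe it are collected but do not enter the model.

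**Working it through.** The documents state no figure for this model, so there is none to reproduce. The check is of what the covariates can carry.

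**1. Coding.** The SAP does not say how the categories are coded. Since the eCRF records only which parameters were considered, used/not used is the only coding that fits.

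**2. Two readings of a tick.**
- *Used to judge presence or absence of activity* (SAP 6.3.2.5). A wet scan leading to q8w and a dry scan leading to q12w both give SD-OCT = 1. The result is lost.
- *Used to judge that activity is present* (SAP section 2). A tick then has direction, but the flags largely restate the activity verdict, which the regimen is meant to follow. Protocol 6.7.2: "In patients with DA, treatment every 8 weeks (q8w) should be considered".

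On neither reading does the model show which finding went with q8w.

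**3. Pooling.** CST, IRF, SRF, sub-RPE fluid, PED volume, SHRM and CRT share one term, so fluid and thickness cannot be told apart within it.

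**4. Illustration (all inputs assumed).** Fluid odds ratio = [p8/(1−p8)] / [p12/(1−p12)], where p8 and p12 are the proportions with fluid in the q8w and q12w groups.
- 60% v 40%: (0.6/0.4)/(0.4/0.6) = 2.25.
- 80% v 20%: (0.8/0.2)/(0.2/0.8) = 16.
- If SD-OCT is ticked at the same rate t (below 1) in both groups, the use odds ratio is [t/(1−t)]/[t/(1−t)] = 1.0 in both cases.

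Now let ticking depend on the finding. Assume the finding is present in 45%, with P(q8w) = 0.768 if present and 0.142 if absent (odds ratio 20).
- Ticked in 90% with the finding, 50% without. P(q8w | ticked) = (0.45×0.9×0.768 + 0.55×0.5×0.142)/(0.405 + 0.275) = 0.515. P(q8w | not ticked) = (0.45×0.1×0.768 + 0.55×0.5×0.142)/(0.045 + 0.275) = 0.230. Use odds ratio = (0.515/0.485)/(0.230/0.770) ≈ 3.6.
- Ticked in 50% with the finding, 90% without. The same steps give 0.337 and 0.645, and a use odds ratio of 0.28.
- Ticked in 70% regardless: 1.0.

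A simulation of 122 patients (2,000 runs) gave median use odds ratios of about 3.7, 0.28 and 1.0, against about 21 for the finding itself. One true effect gives a use odds ratio above, at or below 1 according to ticking habit alone.

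**5. Is a model on values feasible?** BCVA is scheduled at every visit (protocol Table 8-1). The reading centre grades IRF, SRF and CST on study-eye SD-OCT at post-screening visits (SAP 6.3.2.2). The protocol's own covariate rule implies 263 × 0.44 / 12 = 9.6 patients in the smaller outcome group per covariate. The q8w share at Week 16 is not given. Protocol 12.7.1 (56% kept on q12w to Week 48) and 1.1 (more than 80% of those first judged suitable stay on q12w) suggest, indirectly, between 1 − 0.56/0.80 = 30% and 1 − 0.56 = 44%. With at most 122 patients that is 37 to 54. Three terms then have 36.6/3 = 12.2 to 53.7/3 = 17.9 per term, or 9.8 to 14.3 if 20% are lost to unusable images (assumed).

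**The case against.** The strongest reply is that the objective is about reasons, the protocol deliberately recorded only which parameters were used, and protocol 12.5.1 and 12.6 already call for a logistic model of those factors under the word determinants. On this view the model is what was planned and only its label is open to criticism. Most of that stands. The model is legitimate as a description of recorded use, and relabelling it is the main correction.

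Three stronger readings are tempting, and the documents support none of them.
- *The model can show no direction at all.* That depends on an eCRF page not in these documents. On the SAP section 2 wording a tick does have direction. On any wording the odds ratios show whether recorded use goes with q8w or q12w.
- *Pooling SD-OCT is an undeclared deviation.* Protocol 12.5.1 does not fix the covariate coding, itself names OCTA parameters as a group, and leaves details to the SAP. Fourteen separate flags would leave only 36.6/14 = 2.6 to 53.7/14 = 3.8 patients per term on the shares above, so pooling is defensible. Single parameters are still tabulated by regimen.
- *The FA/ICGA flag will be almost empty.* Protocol 8.3.1 says "Fluorescein angiography (FA) and indocyanine green angiography (ICGA) will be performed in both eyes at Screening and Week 48", which makes rarity at Week 16 plausible. But no tick counts are given, activity is judged by clinical practice, and leakage is a listed option.

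It is also fair that reading-centre grades are not what the Investigator relied on. A model using them shows correlates of the choice, not stated reasons.

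**Conclusion.** The concern holds for the interpretation of one secondary regression. The covariates record use of assessment categories, so the odds ratios cannot identify the finding that went with q8w, and the SD-OCT term cannot separate fluid from thickness. This rests on the used/not-used coding, which the SAP does not state but which follows from what the eCRF holds. The size in this trial is unknown: the odds ratios of 2.25, 16, 3.6 and 0.28 come from assumed inputs and show the logic only. The by-regimen tables in SAP 6.3.2.5 and the activity verdict by first regimen in SAP 6.4.1 remain valid. The primary analysis is not touched. The change is worth making because it is cheap and answers objective 5 better.

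**What to change.** 1. Keep the planned model. Report its odds ratios as *association with parameter categories recorded as used for the decision*, not as determinants. State from the eCRF page what a tick means, and reconcile the wordings in protocol section 3 and 8.3.6 and SAP sections 2 and 6.3.2.5.
2. Add one supplementary logistic model of the Week 16 regimen on three Week 16 values: reading-centre IRF or SRF present, CST change from baseline, and BCVA change from baseline. Report how many patients are lost to ungradable images or uncertified instruments.
3. Use Firth penalisation in either model if the data are sparse.
4. Label the supplementary model as added after the interim, which covered all enrolled patients (SAP 6.6), and as showing correlates of the choice.

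Cost: SAP wording and one more model, with no new data. The limits are that the grades are a proxy the Investigator did not see and that unusable images reduce n. OCTA findings and hemorrhage at CFP cannot be added: SAP 1.1 expects most OCTA values to be missing, and protocol 8.3.4 sends only screening CFP for standardized grading.
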